8.0 SAFETY AND ADVERSE EVENT REPORTING REQUIREMENTS

8.1 Reporting Adverse Experiences and Deaths to St. Jude IRB

Only “unanticipated problems involving risks to participants or others” referred to hereafter as “unanticipated problems” are required to be reported to the St. Jude IRB promptly, but in no event later than 10 working days after the investigator first learns of the unanticipated problem. Regardless of whether the event is internal or external (for example, an IND safety report by the sponsor pursuant to 21 CFR 312.32), only adverse events that constitute unanticipated problems are reportable to the St. Jude IRB.

As further described in the definition of unanticipated problem, this includes any event that in the PI’s opinion was:

- Unexpected (in terms of nature, severity, or frequency) given (1) the research procedures that are described in the protocol-related documents, such as the IRB-approved research protocol and informed consent document, as well as other relevant information available about the research; (2) the observed rate of occurrence (compared to a credible baseline for comparison); and (3) the characteristics of the subject population being studied; and
- Related or possibly related to participation in the research; and
- Serious; or if not serious suggests that the research places subjects or others at a greater risk of harm (including physical, psychological, economic, or social harm) than was previously known or recognized.

Unrelated, expected deaths do not require reporting to the IRB. Though death is “serious”, the event must meet the other two requirements of “related or possibly related” and “unexpected/unanticipated” to be considered reportable.

Deaths meeting reporting requirements are to be reported immediately to the St. Jude IRB, but in no event later than 48 hours after the investigator first learns of the death.

The following definitions apply with respect to reporting adverse experiences:

Serious Adverse Event: Any adverse event temporally associated with the subject's participation in research that meets any of the following criteria:

- results in death;
- is life-threatening (places the subject at immediate risk of death from the event as it occurred);
- requires inpatient hospitalization or prolongation of existing hospitalization;
- results in a persistent or significant disability/incapacity;
- results in a congenital anomaly/birth defect; or
- any other adverse event that, based upon appropriate medical judgment, may jeopardize the subject's health and may require medical or surgical intervention to prevent one of the other outcomes listed in this definition (examples of such events include: any substantial disruption of the ability to conduct normal life functions, allergic bronchospasm requiring intensive treatment in the emergency room or at home, blood dyscrasias or convulsions that do not result in inpatient hospitalization, or the development of drug dependency or drug abuse), a congenital anomaly/birth defect, secondary or concurrent cancer, medication overdose, or is any medical event which requires treatment to prevent any of the medical outcomes previously listed.

Unexpected Adverse Event: Any adverse event for which the specificity or severity is not consistent with the protocol-related documents, including the applicable investigator brochure, IRB approved consent form, Investigational New Drug (IND) or Investigational Device Exemption (IDE) application, or other relevant sources of information, such as product labeling and package inserts; or if it does appear in such documents, an event in which the specificity, severity or duration is not consistent with the risk information included therein; or the observed rate of occurrence is a clinically significant increase in the expected rate (based on a credible baseline rate for comparison); or

The occurrence is not consistent with the expected natural progression of any underlying disease, disorder, or condition of the subject(s) experiencing the adverse event and the subject's predisposing risk factor profile for the adverse event.

Internal Events: Events experienced by a research participant enrolled at a site under the jurisdiction of St. Jude IRB for either multicenter or single-center research projects.

External Events: Events experienced by participants enrolled at a site external to the jurisdiction of the St. Jude Institutional Review Board (IRB) or in a study for which St. Jude is not the coordinating center or the IRB of record.

Unanticipated Problem Involving Risks to Subjects or Others: An unanticipated problem involving risks to subjects or others is an event which was not expected to occur, and which increases the degree of risk posed to research participants.

Such events, in general, meet all of the following criteria:

- unexpected;
- related or possibly related to participation in the research; and
- suggests that the research places subjects or others at a greater risk of harm (including physical, psychological, economic, or social harm) than was previously known or recognized. An unanticipated problem involving risk to subjects or others may exist even when actual harm does not occur to any participant.

Consistent with FDA and OHRP guidance on reporting unanticipated problems and adverse events to IRBs, the St. Jude IRB does not require the submission of external events, for example IND safety reports, nor is a summary of such events/reports required; however, if an event giving rise to an IND safety or other external event report constitutes an “unanticipated problem involving risks to subjects or others” it must be reported in accordance with this policy. In general, to be reportable external events need to have implications for the conduct of the study (for example, requiring a significant and usually safety-related change in the protocol and/or informed consent form).

Although some adverse events will qualify as unanticipated problems involving risks to subjects or others, some will not; and there may be other unanticipated problems that go beyond the definitions of serious and/or unexpected adverse events. Examples of unanticipated problems involving risks to subjects or others include:

- The theft of a research computer containing confidential subject information (breach of confidentiality); and
- The contamination of a study drug. Unanticipated problems generally will warrant consideration of substantive changes in the research protocol or informed consent process/document or other corrective actions in order to protect the safety, welfare, or rights of subjects or others.

The principal investigator has the obligation to report all serious adverse events to the FDA and IRB.

The following adverse events that are commonly observed in this patient population will not be reported as individual expedited reports, but with annual continuing review and progress reports:

- Grade 3 or 4 infection or fever
- Grade 3 or 4 fever and neutropenia with or without infection
- Grade 3 or 4 elevation in hepatic transaminases, alkaline phosphatase, GGT, bilirubin, and triglycerides that resolve to less than grade 3 within 5 days
- Grade 3 or 4 elevation of amylase or lipase
- Grade 3 electrolyte disturbances and Grade 4 electrolyte disturbances that resolve to < grade 3 within 24 hours allowing for replacement as needed
- Grade 3 and 4 electrolyte disturbances due to tumor lysis

- Grade 3 hyperglycemia or hypoglycemia and Grade 4 hyperglycemia or hypoglycemia that resolve to < grade 3 within 24 hours, allowing for replacement or insulin as needed
- Grade 3 fatigue and nausea.
- Grade 3 vomiting or diarrhea that resolves to ≤ Grade 2 within 7 days with supportive care as needed (antiemetics, antidiarrheal medications)
- Grade 3 or 4 hypotension explained by sepsis, pancreatitis, or infusion reaction
- Grade 3 mucositis that resolves to ≤ Grade 2 within 14 days
- Grade 3 anorexia
- Grade 3 hypertension
- Grade 3 enterocolitis, typhlitis, or colitis
- Grade 3 gastric hemorrhage, gastric ulcer, gastritis, and/or upper GI bleed
- Grade 3 glucose intolerance
- Grade 3 leukoencephalopathy and/or seizures secondary to intrathecal chemotherapy
- Any Grade 3 event not specified above as an exception which resolves within 48 hours
- Any Grade 3 event secondary to an infectious process or thrombocytopenia

This is an investigator-initiated study. The principal investigator, [name] and St. Jude are conducting the study and acting as the sponsor. Therefore, the legal/ethical obligations of the principal investigator include both those of a sponsor and those of an investigator.

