Brief Outline of Treatment Plan: Patients will be randomized on day 4 of induction therapy to either conventional or intensive blood pressure goals. Patients will be treated with the long-acting antihypertensive lisinopril to achieve blood pressure control as indicated by their randomized arm. Long-acting therapy will be adjusted every 3-4 days as needed to achieve targeted control based on the median of blood pressures obtained in that period. Treatment of hypertension to the target will continue until the completion of reinduction II therapy. Patients will be evaluated for osteonecrosis as indicated in their primary therapeutic protocol using MRI during reinduction II.
Study Design: Randomized unblinded trial of conventional vs. intensive hypertensive control. Evaluation of the MRIs defining the primary endpoint will be performed by a blinded radiologist.
Sample Size: We will randomize 160 evaluable patients (180 total).
Data Management: Data management and statistical analysis will be provided locally by the Comprehensive Cancer Center Hematological Malignancies Program and the Biostatistics Department at St. Jude Children’s Research Hospital.
Human Subjects: The risks to subject will be related to the toxicity of antihypertensive therapy. Side effects are anticipated to be mild and limited to reversible orthostatic/postural hypotension and transient increases in creatinine. Patients will be informed of this and other minor side effects during informed consent discussion. Adverse events will be monitored and reported and treated appropriately.

TABLE OF CONTENTS

1.0	OBJECTIVES	1
1.1	Primary Objective	1
1.2	Secondary Objectives	1
1.3	Exploratory Objectives	1
2.0	BACKGROUND AND RATIONALE	2
2.1	Background	2
2.2	Rationale	2
2.3	Background and Rationale for Ancillary and Exploratory Studies	3
3.0	RESEARCH PARTICIPANT ELIGIBILITY CRITERIA AND ENROLLMENT	4
3.1	Inclusion Criteria	4
3.2	Exclusion Criteria	4
3.3	Research Participant Recruitment and Screening	5
3.4	Enrollment on Study at St. Jude	5
3.5	Enrollment Instructions for Collaborating Sites	5
4.0	TREATMENT PLAN	6
4.1	Treatment	6
4.2	Participation of St. Jude Affiliates in the Treatment Plan	9
4.3	Treatment Modifications for Collaborating Sites	9
4.4	Supportive Care	9
4.5	Symptom Survey and Semi-structured Interviews	10
5.0	REQUIRED EVALUATIONS, TESTS, AND OBSERVATIONS	12
5.1	Pre-Study Evaluations	12
5.2	Evaluations during Therapy	12
5.3	Response Evaluations	13
5.4	Off-Study Evaluations	13

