2.2 Rationale

Based on the retrospective clinical and prospective preclinical data, undertreatment of hypertension is associated with an approximately 2-fold increased risk of developing osteonecrosis after accounting for other known risk factors. Data from both adult^{14,15} and pediatric¹⁶ populations shows a benefit to more intensive blood pressure control compared to conventional control. Due to the risks of complications from untreated hypertension (e.g. posterior reversible encephalopathy syndrome), it is both impractical and unethical to randomize patients to no treatment for their hypertension. We will therefore test the efficacy of intensive hypertensive control (targeted to the 50-75th

percentile for age, sex, and height, systolic) compared to conventional antihypertensive control (targeted to the 90-95th percentile for age, sex, and height, systolic). We have chosen slightly higher systolic blood pressure goals for the intensive arm compared to the ESCAPE trial¹⁶ due to the presence of anemia and risk for infection in pediatric ALL patients, both of which may predispose to an increased risk of symptomatic hypotension.

The Children's Oncology Group AALL0232 and CCG1961 trials demonstrated differences in osteonecrosis in patients receiving dexamethasone instead of prednisone during induction, or continuous instead of alternate week dexamethasone during delayed intensification, respectively.^{2,5} These data support the critical role that these two steroid-intensive phases of therapy (termed induction and reinduction in St. Jude Total Therapy protocols) play in the development of osteonecrosis. The planned intervention will therefore encompass these two periods.

Although TOT17 includes an optional randomization for vincristine and dexamethasone duration (49 weeks vs. 101 weeks), the primary endpoint in this study (Reinduction II MRI) occurs prior to that randomization. Thus, the randomization will not impact the primary outcome of the study. Furthermore, review of symptomatic osteonecrosis timing on TOTXVI suggests that the majority of patients develop symptoms prior to this timepoint. For secondary endpoints including CTCAE symptomatic osteonecrosis, we will consider dexamethasone duration as a covariate.

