Intensive Low End Target (mmHg)	110						
Intensive High End Target (mmHg)	120						

Patients will begin antihypertensive therapy to achieve the targeted blood pressure on Day 4 of Remission Induction on TOT17. Patients already receiving antihypertensive therapy prior to Day 4 should have their therapy adjusted according to the guidelines below.

During outpatient visits, blood pressures measured should be performed after the patient has been sitting at rest for at least 10 minutes and is not experiencing pain or anxiety.

During induction, blood pressure adjustments will be made for each patient based on the mean blood pressure over the preceding 4 days (minimum 2 measurements) unless indication for immediate change is met (listed below). Blood pressures obtained while a patient is sedated for procedures should not be included in the evaluated blood pressures when determining whether to adjust antihypertensive medications. Patients with mean blood pressures outside of the target range should have antihypertensive therapy adjusted in an attempt to reach the goal range. However, if prior changes to medication have been made within 7 days and blood pressures are both 1) closer to the target range than at the time of prior medication change and 2) within 10mmHg of the goal range following that change, further modifications can be delayed until a subsequent visit.

Immediate changes to antihypertensive therapy are indicated if:

- 1) systolic pressures are more than 15mmHg above the high end target,
- 2) patients are experiencing headache, vision changes, or neurologic symptoms attributable to hypertension,
- 3) the patient has experienced an episode of syncope,
- 4) the patient's systolic pressure is below 90, or
- 5) the patient is experiencing unacceptable toxicity from their current antihypertensive therapy.

Patients will continue antihypertensive therapy (as needed to achieve the targeted blood pressure range) during phases of therapy with scheduled glucocorticoids (i.e. Induction and Continuation, including Reinduction 1 & 2). Patients should continue antihypertensive therapy during other phases if tolerated. Caution is warranted in consolidation (due to the risk of altered renal perfusion or kidney injury) and during immunotherapy (due to the risk of cytokine release induced hypotension).

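### The Section 8.1 exemption list is not adapted to a blood-pressure-lowering trial: it defers short Grade 3 hypotension even when drug-caused, and hypotension to which the antihypertensive may have contributed alongside sepsis or infection

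*Combined protocol and SAP*

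**What the plan says.** Section 8.1 sets out events, described as common in this population, that "will not be reported as individual expedited reports, but with annual continuing review and progress reports". Three lines bear on hypotension:

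- the hypotension line: "Grade 3 or 4 hypotension explained by sepsis, pancreatitis, or infusion reaction";
- the 48-hour clause: "Any Grade 3 event not specified above as an exception which resolves within 48 hours";
- the infection clause: "Any Grade 3 event secondary to an infectious process or thrombocytopenia".

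None of them makes an exception for events possibly related to the antihypertensive.

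Elsewhere the protocol treats hypotension as a risk of the intervention. Section 2.2 explains that the intensive-arm goals were set somewhat higher than in an earlier paediatric trial because of the "presence of anemia and risk for infection in pediatric ALL patients, both of which may predispose to an increased risk of symptomatic hypotension". Section 4.1 allows antihypertensives to continue outside the glucocorticoid phases if tolerated, but urges caution "during immunotherapy (due to the risk of cytokine release induced hypotension". The Protocol Summary, under Human Subjects, states: "Side effects are anticipated to be mild and limited to reversible orthostatic/postural hypotension and transient increases in creatinine".

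Section 8.1 also states two general duties. At its start, only unanticipated problems are reportable to the IRB, within 10 working days. Just before the exemption list, the principal investigator must report all serious adverse events to the FDA and IRB.

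**The concern.** Lowering blood pressure is the intervention, so severe hypotension is the most direct way it could do harm. The setting the protocol worries about has two causes acting together: an antihypertensive, plus infection or cytokine release. An exemption that applies once another cause explains the event suits a general leukaemia trial. Here it can remove the joint-cause event. The 48-hour clause goes further, because it ignores cause altogether: the condition on cause in the hypotension line has no effect for a short Grade 3 episode.

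At stake is how soon the IRB sees individual cases of a harm the protocol itself anticipates. The trial is open-label, so whoever judges whether sepsis explains an episode knows the arm.

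**Working it through.** The plan gives no figure to reproduce on this point. The check sets the clauses side by side.

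**Step 1. Sort hypotension by the wording of the Section 8.1 list.**

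| Event | Deferred to annual reporting by the list? |
|---|---|
| Grade 3 or 4, explained by sepsis, pancreatitis or infusion reaction | Yes |
| Grade 3, drug-caused, resolved within 48 hours | Yes, by the 48-hour clause |
| Grade 3, secondary to infection | Yes, by the infection clause |
| Grade 3, drug-caused, over 48 hours, no listed cause | No |
| Grade 4, drug-caused, no listed cause | No |

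Cytokine-release hypotension falls in the first row only if it is classed as an infusion reaction. The documents do not say whether it is.

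**Step 2. Ask which other routes catch the deferred events.**

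- *Unanticipated problems (8.1).* The event must be unexpected and at least possibly related. Section 8.2 defines possibly related as more likely explained by study treatment than by other drugs, interventions or underlying conditions. An episode in which sepsis is the larger cause and the antihypertensive a contributor fails that test. Section 8.2 does count unlikely-related events as treatment-related, but for safety analyses only.
- *Collaborating sites to the lead investigator (8.3).* This covers events that are both serious and unexpected, within 48-72 hours.
- *Suspension rule (10.3).* It counts Grade 3 or higher acute kidney injury not resolving to Grade 0-1 within 72 hours, and syncope with injury, in glucocorticoid phases only. Hypotension is not a targeted toxicity.
- *Monthly summaries (9.1).* These go to the principal investigator and Biostatistics at least monthly. They are not stated to be by arm. Section 9.1 specifies recording of non-haematologic Grade 3-5 events during glucocorticoid phases, whereas 6.2 and 8.2 describe documentation more broadly. Whether hypotension during immunotherapy reaches the summary is therefore unclear.

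**Step 3. Test what the list exempts events from.** If only unanticipated problems are reportable, joint-cause hypotension is already excluded by the relatedness definition, and leaving the list would not by itself bring it in. If all serious adverse events go to the FDA and IRB, the list removes serious events from individual reporting. Section 8.1 states both duties and does not say which governs, or whether the list overrides the unanticipated-problem duty.

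**Step 4. Exposure during one annual cycle.** Section 10.1 gives about 60 randomised a year, 180 in total, and accrual within 3.5 years.

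- Intensive arm, total: 180 / 2 = 90.
- At the stated annual rate: 60 / 2 = 30 a year; 30 / 90 = 33%.
- At the pace implied by 3.5 years: 180 / 3.5 = 51.4 a year; 51.4 / 2 = 25.7, about 26; 25.7 / 90 = 29%.

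These are patients randomised, not events.

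**The case against.** The strongest reply is that Section 8.1 already covers an excess. It defines unexpected in terms of nature, severity or frequency, judged against a credible baseline, and it treats a clinically significant rise over the expected rate as unexpected. Section 8.3 asks the principal investigator whether an expected event is occurring significantly more often or more severely than expected. Nothing says the exemption list overrides these clauses. A reader might infer that an excess of severe hypotension in the intensive arm could surface only at annual review; the documents do not support that. What remains is narrower: the frequency clauses work only if someone counts the events against a baseline, and the documents give no hypotension rate and no by-arm tabulation.

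A reader might also infer that all hypotension from tighter control waits for the annual report. The last two rows of the table in the working show otherwise, and the quoted hypotension line concerns causes other than the study drug.

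It can also be said that individual reports are a poor way to see a difference between arms, and that requiring one for every septic episode, whatever its explanation, sits badly with the rule that only unanticipated problems are reportable. Both points stand. They limit any individual-report requirement to cases with a possible drug contribution and favour a by-arm table for the rest.

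**Conclusion.** The point holds as a gap in the reporting rules. The list has no exception for the intervention under test: it defers short Grade 3 hypotension that the antihypertensive caused, and hypotension in which the antihypertensive may have acted together with sepsis, pancreatitis, infusion reaction or infection. The relatedness definition in 8.2 means that joint-cause events can also miss the unanticipated-problem route.

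Only individual expedited reporting is deferred, by at most the interval to the next annual review. Internal review at least monthly continues. The number of events affected cannot be estimated from the documents; the exposure is about 26 to 30 intensive-arm patients randomised per year, if randomisation is 1:1 and accrual runs between the two paces in Section 10.1. The primary endpoint and its analysis are unaffected. The change is worth making because it is cheap and improves safety oversight.

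**What to change.** These changes concern reporting only; they set no clinical rule.

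1. In Section 8.1, state that the exemptions, including the 48-hour and infection clauses, do not apply to serious Grade 3-4 hypotension in a participant taking a HYPERION antihypertensive at onset when a contribution from the antihypertensive cannot be excluded, even if another cause is also present.
2. In the monthly toxicity summary in Section 9.1, tabulate all Grade 3-4 hypotension by arm, whatever its explanation and in every phase in which antihypertensives are given. Align the recording rule in 9.1 so that those phases are captured.
3. Reconcile the two statements in Section 8.1: that only unanticipated problems are reportable, and that all serious adverse events go to the FDA and IRB. Leaving the list does not by itself make an event expedited, so the reconciled text should say which route the events in item 1 take.

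The cost is a short amendment to 8.1 and 9.1, one more table in a summary that already exists, and a few extra individual reports a year. The exact number is unknown, and some will concern sepsis-related hypotension that would have occurred anyway.
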